6.3. Follow-up Period

6.3.1. 30-Day Follow-up After Last Dose Visit (+ 7 days)

All subjects will be followed for 30 days after the last dose of study treatment for AE reporting, as well as any SAEs made known to the Investigator at any time thereafter that are suspected of being related to study treatment, as described in Section 10.1.

The following will be performed as specified in the Table of Events (Section 5.1, Table 3):

- **Concomitant medications and procedures:** As detailed in Section 6.1
- **Vital signs, Physical exam and weight:** As detailed in Section 6.1
- **Electrocardiogram (ECG):** As clinically indicated (detailed in Section 6.1)
- **Pregnancy testing:** As detailed in Section 6.1
- **Hematology:** As detailed in Section 6.1
- **Serum Chemistry:** As detailed in Section 6.1
- **Coagulation:** As clinically indicated (detailed in Section 6.1)
- **Urinalysis:** As clinically indicated (detailed in Section 6.1)

- **Thiamine level:** As clinically indicated (detailed in Section 6.1)
- **Transfusion burden assessment:** As detailed in Section 6.2
- **Cognitive assessment - Mini-Mental State Examination:** As clinically indicated (detailed in Section 6.1)
- **Survival:** Refer to Section 6.3.2
- **Progression of myelofibrosis to acute myeloid leukemia (AML) assessment:** Refer to Section 6.3.2 and Section 10.7
- **Subsequent therapies for disease under study:** Refer to Section 6.3.2
- **Spleen size by palpation:** As detailed in Section 6.1
- **Eastern Cooperative Oncology Group (ECOG) performance status:** As detailed in Section 6.1
- **Adverse events:** Refer to Section 6.1
- **Risk mitigation for Gastrointestinal toxicity & Encephalopathy including Wernicke:** Refer to Section 7.3 and Section 7.4.
- **Symptoms response assessment:** as detailed in Section 6.7.1
- [REDACTED]

6.3.2. Survival Follow-up

All subjects discontinued from protocol-prescribed therapy for any reason will be followed for survival, subsequent therapies, new malignancy and progression of myelofibrosis to acute myeloid leukemia (AML) every 3 months until death, up to 12 months after EOT, lost to follow-up, withdrawal of consent for further data collection, or study closure whichever comes first. See Section 10.7 for additional details on reporting.

A window of \pm 14 days is allowed for post treatment Survival Follow-up assessments; the visits should be performed every 3 months \pm 14 days and can be done by a documented telephone contact between site and subject.

6.4. Unscheduled Assessments or Visits

Should it become necessary to repeat an evaluation (eg, laboratory tests, vital signs, etc.) outside of scheduled study visits, or to perform additional evaluations than the ones described in the current protocol, the results of these additional evaluations should be recorded in an unscheduled visit eCRF page(s). These evaluations should also appear in the subject's chart and/or other source documentation.

In the event that immediate hematology/biochemistry/urinalysis/coagulation/thiamine/lipid values are needed for clinical decisions, local laboratory results may be used pending the outcome of the central laboratory assessment. However, matching samples must always be sent to the central laboratory and clinical decisions and assessments must be reconciled with the

results of the central laboratory. The results of these additional analyses will be recorded in the subjects' eCRF as applicable as described in Section 10.

6.5. Response Assessment

Response assessments should occur at the end of C3, C6, C12, C18, C24, and EOT (and at the end of every 6th cycle [24 weeks]) as applicable afterwards. The response assessment can be combined with the Day 1 visit of the subsequent cycle or End of Treatment visit. The following assessments will be performed:

- **Symptoms response assessment:** Refer to Section 6.7.1
- **Spleen volume by MRI/CT scan:** Refer to Section 6.1
- **Spleen size by palpation:** Refer to Section 6.1

If a bone marrow assessment is performed as per standard of care, in addition to the assessments described above, the Investigator will assess response, for example, in terms of CR, PR, relapse, cytogenetic and molecular response as per IWG-MRT 2013 (Tefferi, 2013).

- [REDACTED]

6.7. Subject Reported Outcomes

All PRO evaluations will be performed on an electronic tablet at the site. These assessments should be performed before any other assessments are performed by the Investigator or designee during the visit.

6.7.1. Symptoms Response Assessment

The MF-related symptoms evaluation will be performed using the MFSAF v.4.0 version using a 7-day recall period (Gwaltney, 2017).

This questionnaire assesses 7 key MF-associated symptoms (night sweats, pruritus, abdominal discomfort, early satiety, pain under ribs on left side, bone or muscle pain, and fatigue). Due to the number of different questionnaires used in clinical trials for patient-reported MF symptoms, this version was developed following harmonization work conducted in collaboration with industry and the FDA with the aim to create a publicly available, consensus -based and

harmonized version of MF symptoms questionnaire ([Gwaltney, 2017](#)). The MFSAF version 4.0. was validated and recommended to be used in clinical trials to assess MF symptoms.

The Total Symptom Score is a composite score defined as the sum of each of the 7 symptom scores. To allow indirect comparison with previous MF studies, a modified Total Symptom Score ([Mesa, 2013](#)) will also be derived from the 6 symptoms considered (night sweats, pruritus, abdominal discomfort, early satiety, pain under ribs on left side, bone or muscle pain).

The MF-related symptoms evaluation will be performed at the site at screening, on Day 1 of each treatment cycle (and for Response Assessments), at the EOT and the 30-Day Follow-up after last dose visit. If exceptional circumstances preclude the continued administration of measures using planned modalities, then alternate administration methods may be required.

A copy of the questionnaire is presented in [Appendix B](#).

A large black rectangular box covers the majority of the page below the text, indicating that the questionnaire described in the text has been redacted.

7. DESCRIPTION OF STUDY TREATMENTS

7.1. Description of Investigational Products

7.1.1. Fedratinib

The Sponsor will supply fedratinib 100 mg capsules in high density polyethylene (HDPE) bottles for oral administration and will be labeled appropriately as investigational product for this study.

The study drug must be kept at the temperature condition as specified on the label. Fedratinib must be stored at temperatures below 30°C.

Other recommended/required concomitant medications per the protocol will be provided by the site. Celgene will not provide these medications.

7.2. Treatment Administration and Schedule

Fedratinib

Fedratinib will be dispensed to subjects using the IRT system. The fedratinib dose is 400 mg/day PO (4 x 100 mg capsules) to be self-administered orally once daily continuously on an outpatient basis, preferably together with an evening meal, the same time each day. However, fedratinib may be taken with or without regard to food. In case a dose is missed, the next dose should be taken the following day at the same time of day as previously taken before the dose was missed.

A flexible dose modification regimen may be employed to minimize drug toxicity for individual subjects, with possible daily doses of 100 mg, 200 mg, 300 mg, or 400 mg. For subjects with severe impairment of renal function and co-administration of strong or moderate CYP3A4 inhibitors the fedratinib dose is adjusted (Refer to Section 7.2.2 and Section 7.2.3).

For administrative purposes cycles are defined as 4-week (28-day) periods. Subjects may continue treatment with fedratinib until one of the conditions described in the “Treatment Period” section of Section 3.1 occurs.

All study subjects will receive thiamine supplementation (Refer to Section 7.4.3).

7.2.1. Fedratinib Dose Modification for Toxicity

The most common adverse events associated with fedratinib are hematological and gastrointestinal events. Hematological adverse events associated with JAK2 inhibitors are dose dependent, mechanism-based and are managed through dose reductions, dose interruptions and transfusions.

The Fedratinib Dose Modification table (Table 4) should only be used for events attributed to fedratinib treatment or if the AE cannot be attributed by the investigator to an identifiable cause such as underlying illness or disease progression, other concurrent illness, or concomitant medication.

If a subject experiences a drug toxicity as specified in the table below, the dosing must be interrupted; in some cases (ie, when it is not a liver function test (LFT) abnormality) the dose can be titrated by a 100 mg/day decrement during the study, depending upon the Investigator's judgment, down to a minimum dose of 200 mg/day. For subjects with severe impairment of renal

function and co-administration of strong or moderate CYP3A4 inhibitors the fedratinib dose is adjusted (Refer to Section 7.2.2 and Section 7.2.3). In addition, if a subject experiences a dose interruption of fedratinib for more than 28 consecutive days, consultation with the Medical Monitor is required to determine if study treatment may resume.

If a subject does not tolerate fedratinib therapy after 2 dose level reductions from the starting dose, he/she must be withdrawn from the study treatment. If the toxicity does not resolve in the time period as specified in the table below the subject must be withdrawn from the study treatment. Reescalation of doses is possible in certain cases. The daily dose of fedratinib cannot exceed 400 mg/day.

Table 4: Fedratinib Dose Modification Schedule

Adverse Event	Fedratinib Management	Recovery	Fedratinib Dose After Recovery
Hematological			
Grade 4 or Grade 3 thrombocytopenia with major bleeding	Hold fedratinib up to 28 days	Grade \leq 3 thrombocytopenia without bleeding	Dose decrement by 1 dose level: 100 mg/daily decrease
Grade 4 neutropenia	Hold fedratinib up to 28 days	Grade \leq 2 neutropenia	Dose decrement by 1 dose level: 100 mg/daily decrease
Grade 4 hematological toxicity with dose reduction in subsequent cycle	-	Toxicity resolves for at least 1 cycle	Subsequent upward dose titration possible of 1 dose level (100 mg daily) per cycle as per the Investigator's discretion
Recurrence of a Grade 4 hematological toxicity	-	-	Subsequent upward dose titration not permitted Fedratinib discontinuation as per the Investigator's discretion
Non-hematological			
Non-hematological Grade 4 or unmanageable Grade 3 toxicity after already dose reducing in the previous cycle	-	-	Subsequent upward dose titration not permitted Consider fedratinib discontinuation as per the Investigator's discretion

Table 4: Fedratinib Dose Modification Schedule (Continued)

Adverse Event	Fedratinib Management	Recovery	Fedratinib Dose After Recovery
Hepatic (LFT abnormalities)			
Grade \geq 3 AST or ALT or total bilirubin	Hold fedratinib Weekly monitoring of LFTs, until resolution, After fedratinib resumed, LFT monitoring every 2 weeks for the 3 subsequent cycles at a minimum	Grade \leq 1	Fedratinib Hold \leq 14 days: Dose decrement by 1 dose level: 100 mg daily decrease, Subsequent upward dose titration not permitted Fedratinib Hold $>$ 14 days (AE did not return to Grade \leq 1): Fedratinib permanently discontinued Grade 4 in the absence of demonstrable cause: permanently discontinue fedratinib
Recurrence of LFT abnormality (ie, \geq Grade 3 toxicity) after dose reduction	Discontinue fedratinib permanently	-	-
Gastrointestinal			
Grade 2 nausea, vomiting, diarrhea, or constipation that does not respond to adequate therapeutic or supportive measures within 48 hours	Hold fedratinib up to 14 days	Toxicity resolves to Grade \leq 1	Consider resuming the dose at the same level after resolution of adverse event (see section on management of GI toxicity)
Grade \geq 3 or recurrence of Grade 2 nausea, vomiting, diarrhea, or constipation that does not respond to adequate therapeutic or supportive measures within 48 hours	Hold fedratinib up to 14 days	Toxicity resolves to Grade \leq 1	Consider reducing one dose level after resolution of adverse event (see section on management of GI toxicity below)
Other Adverse Events Not Described Above			
Grade \geq 3 non-hematological toxicity, non-gastrointestinal toxicity or Grade \geq 2 peripheral neuropathies	Hold fedratinib up to 14 days	Toxicity resolved to Grade \leq 1	Dose decrement by 1 dose level: 100 mg daily decrease
In case of a potential case of encephalopathy including Wernicke's refer to Section 7.4, Management of encephalopathy, including Wernicke's.			

AE = adverse event; ALT = alanine aminotransferase; AST = aspartate aminotransferase; GI = gastrointestinal; LFT = liver function test.

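### Section 7.2.1 excludes liver function test abnormalities from the 100 mg/day decrement, but the hepatic rows of Table 4 prescribe that decrement for a first Grade 3 or higher event that recovers within 14 days

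*Combined protocol and SAP*

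**What the plan says.** Section 7.2.1 of the protocol sets a general rule and then gives Table 4. The rule opens with its scope: "If a subject experiences a drug toxicity as specified in the table below, the dosing must be interrupted". The same sentence goes on to say that "in some cases (ie, when it is not a liver function test (LFT) abnormality) the dose can be titrated by a 100 mg/day decrement", at the Investigator's judgment and with a floor of 200 mg/day. Section 7.2.1 also confines Table 4 to events attributed to fedratinib, or events for which the Investigator cannot identify another cause.

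Table 4 has a block headed "Hepatic (LFT abnormalities)", whose first row is triggered by Grade 3 or higher AST, ALT or total bilirubin. It gives these outcomes:

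- Recovery to Grade 1 or lower with a hold of 14 days or less: "Dose decrement by 1 dose level: 100 mg daily decrease, Subsequent upward dose titration not permitted".
- Hold longer than 14 days without that recovery: permanent discontinuation.
- Grade 4: "Grade 4 in the absence of demonstrable cause: permanently discontinue fedratinib".

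The next row covers recurrence of a Grade 3 or higher LFT abnormality once the dose has been reduced. Its instruction is "Discontinue fedratinib permanently".

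**The concern.** The general sentence and the hepatic rows cover the same events and give different answers on whether a 100 mg decrement is available. A site that reads the sentence finds LFT events excluded from the decrement. A site that reads the table finds the decrement prescribed.

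Four things in the protocol make this worth correcting:

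- Section 10.7.1 lists Grade 3 or 4 ALT, AST or total bilirubin elevation as an adverse event of special interest (AESI), so the conflict falls on events that the protocol singles out.
- The recurrence row depends on an earlier dose reduction. If none was made, it is unclear whether a second event falls under that row.
- Section 6 allows no waivers or deviations. With two current rules, a site that follows one departs from the other.
- Sections 9.7.1 and 9.7.2 report dose reductions with their reasons, and treatment-emergent events leading to reduction, interruption or discontinuation. Uneven handling of LFT events would carry into those summaries.

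**Working it through.** No sample size, power or event count is involved, so the check is a comparison of the two passages.

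**Step 1: do they cover the same events?** Yes. The sentence applies to toxicities specified in Table 4, and the hepatic block of Table 4 is labelled as LFT abnormalities. The category that the parenthesis excludes is the category named in the block heading.

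**Step 2: what does the parenthesis do?** It uses *ie*, not *eg*. It therefore defines the cases in which the decrement is available and does not merely illustrate them. LFT abnormalities are outside the definition.

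**Step 3: what does the table do for those events?**

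| Hepatic event (Grade 3 or higher) | Table 4 | Section 7.2.1 sentence |
|---|---|---|
| First event, recovers to Grade 1 or lower, hold of 14 days or less, not Grade 4 without demonstrable cause | One-level (100 mg) decrement, no later upward titration | Interrupt; decrement not available; no restart dose given |
| Hold longer than 14 days without recovery | Permanent discontinuation | No conflict over the decrement |
| Grade 4 without demonstrable cause | Permanent discontinuation | No conflict over the decrement |
| Recurrence after dose reduction | Permanent discontinuation | The reduction that the row presupposes is excluded |

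The direct conflict is confined to the first row of this comparison. The last row is affected indirectly, because its trigger assumes that the first was applied.

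**Step 4: is either passage superseded or damaged?** No. Both are in the body of the current protocol, not in an amendment summary. Neither is redacted, and the hepatic rows are legible.

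**Step 5: size of the step that the table prescribes.** From 400 mg/day, 100/400 = 25%. From 300 mg/day, 100/300 = 33%. These figures describe the table's decrement only. They are not a measured difference between sites, because the text supplies no restart dose to compare with.

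**The case against.** **The sentence may concern discretionary, stepwise titration.** It says that the dose can be lowered at the Investigator's judgment, down to 200 mg/day. On this reading LFT events are set apart because Table 4 gives them a fixed single step with no return upward, and the two passages are compatible. The discretion wording is there, but the reading does not reconcile the passages. Table 4 also words the decrements for thrombocytopenia, neutropenia and other Grade 3 or higher toxicity without discretion, so discretion does not separate LFT from non-LFT events. The sentence also excludes LFT events from a 100 mg/day decrement as such, not only from a second one.

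**Table 4 is the operative instruction.** The Protocol Summary sends sites to Table 4 for interruption, modification and re-escalation, Section 7.2.1 relies on it for resolution times, and Section 11.1 ties discontinuation to it. The hepatic row is specific on hold, recovery, monitoring and restart. This stands: it makes divergent practice less likely and limits the severity. It does not remove the contradictory sentence.

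**Stronger readings that the documents do not support.** A reader might infer that a site following the text would resume at the same dose. The text gives no restart dose for LFT events, and a reading of no restart is equally open. A reader might also extend the conflict to every Grade 3 or higher LFT event that resolves within 14 days. Table 4 discontinues for Grade 4 without demonstrable cause and for recurrence after reduction, and it does not apply at all to events with another identified cause. Lastly, a general 25% dose difference would hold only for subjects at 400 mg/day, and only if a same-dose restart were assumed.

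**Conclusion.** Wrong as written: an internal inconsistency. Section 7.2.1 excludes LFT abnormalities from the decrement that the hepatic rows of Table 4 prescribe.

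Its extent is one class of event, the first-row case in the comparison above, in subjects whose event is attributed to fedratinib or has no other identified cause. A second effect is uncertainty over the recurrence row when no reduction was made. The documents give no expected number of such events, so the number of subjects affected cannot be stated.

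The conclusion rests on reading *ie* in its ordinary defining sense. No effect on sample size, power or the primary analysis is shown. What is at stake is consistent handling of an AESI and consistent reporting of dose reductions and discontinuations. That supports a correction that should be made, at moderate rather than high severity. No view is taken on which rule is clinically right.

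**What to change.** Reconcile the parenthesis in Section 7.2.1 with the hepatic rows of Table 4, including the recurrence row, so that one rule remains for LFT abnormalities. The sponsor decides which. Whichever rule is kept, the wording should make clear when the recurrence row applies.

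The cost is rewording one parenthesis, or the matching table rows, in a protocol amendment. No change is needed to the sample size or the planned analyses.

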7.2.2. Fedratinib Dose Adjustment for Co-administration with Strong CYP3A4 Inhibitors

Concomitant administration of fedratinib with strong CYP3A4 inhibitors increases fedratinib exposure. Increased fedratinib exposure may increase the risk of AEs. In place of strong

CYP3A4 inhibitors, consider alternative therapies that do not strongly inhibit CYP3A4 activity. If strong CYP3A4 inhibitors cannot be replaced, reduce fedratinib dose to 200 mg when administering with strong CYP3A4 inhibitors, (eg, ketoconazole, ritonavir; refer to [Appendix L](#)). Additional dose adjustments (decrease or increase of the daily dose) should be made with monitoring of fedratinib-related safety (Section [7.3](#)) and efficacy.

In cases where co-administration with a strong CYP3A4 inhibitor is discontinued, the fedratinib dose should be increased to 300 mg daily during the first 2 weeks after discontinuation of the CYP3A4 inhibitor, and then to 400 mg daily thereafter as tolerated. Additional dose adjustments should be made as needed based upon frequent monitoring of safety.

In all the situations above, please contact the sponsor Medical Monitor for any question or guidance.

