Study population consists of subjects with intermediate or high-risk primary myelofibrosis (PMF), post-polycythemia vera myelofibrosis (post-PV MF), or post-essential thrombocythemia myelofibrosis (post-ET MF).

Length of Study

The expected duration of the study is approximately 4 years, which includes approximately 18 months to fully enroll, and 24 months for treatment and follow-up. Actual duration of the trial will be dependent upon the median treatment duration for subjects.

The End of Trial is defined as either the date of the last visit of the last subject to complete the Survival Follow-up (or Long-term Follow-up), or the date of receipt of the last data point from the last subject that is required for primary, secondary, [REDACTED] analysis, as prespecified in the protocol, whichever is the later date.

Study Treatments

Fedratinib will be orally self-administered on an outpatient basis, once daily preferably together with food during an evening meal at the same time each day in consecutive 4-week (28-day) cycles. However, fedratinib may be taken with or without regard to food.

The fedratinib dose in this study is 400 mg/day. If a subject experiences a drug toxicity as specified in the Fedratinib Dose Modification Schedule table ([Table 4](#)), the dosing should be interrupted and the dose may need to be modified ([Section 7](#)).

If a subject does not tolerate fedratinib therapy after 2 dose level reductions from the starting dose, he/she must be withdrawn from the study treatment. If the toxicity does not resolve in the time period as specified in the Fedratinib Dose Modification Schedule table ([Table 4](#)), subjects must be withdrawn from the study treatment. Reescalation of doses is possible in certain cases as defined in the Fedratinib Dose Modification Schedule table ([Table 4](#)). The daily dose of fedratinib cannot exceed 400 mg/day.

Subjects may continue treatment with fedratinib until unacceptable toxicity, lack of therapeutic effect, progression of disease, or until a subject is not compliant with treatment or withdraws consent.

Overview of Key Efficacy Assessments

Assessment of Spleen Size

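### Section 7.2.2 returns fedratinib to 400 mg after a strong CYP3A4 inhibitor is stopped, without making that step subject to Table 4's bars on upward titration

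*Combined protocol and SAP*

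**What the plan says.** Section 7.2.2 covers subjects whose strong CYP3A4 inhibitor cannot be replaced. Fedratinib is lowered to 200 mg during co-administration. When the inhibitor is withdrawn, "the fedratinib dose should be increased to 300 mg daily during the first 2 weeks after discontinuation of the CYP3A4 inhibitor". The last step of the return rule reads "and then to 400 mg daily thereafter as tolerated". The section then adds: "Additional dose adjustments should be made as needed based upon frequent monitoring of safety". It closes by inviting sites to contact the Medical Monitor with questions. It mentions neither Table 4 nor the dose held before the inhibitor.

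Table 4 (Section 7.2.1) rules out upward titration in three rows:

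- Grade 3 or higher AST, ALT or total bilirubin, where the dose after recovery is a "100 mg daily decrease, Subsequent upward dose titration not permitted".
- "Recurrence of a Grade 4 hematological toxicity".
- "Non-hematological Grade 4 or unmanageable Grade 3 toxicity after already dose reducing in the previous cycle".

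Section 7.2.1 refers the reader to 7.2.2 and 7.2.3 for dose adjustment with CYP3A4 inhibitors but does not rank the rules. Section 8.3.1 only refers back to 7.2.2.

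**The concern.** The return rule in 7.2.2 is written for every subject who stops a strong inhibitor. It suits a subject who was on 400 mg beforehand. It does not suit a subject whose dose Table 4 has already lowered and fixed because of toxicity: 7.2.2 then directs an increase that Table 4 forbids.

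The matter at stake is subject safety and consistent dosing across sites. Section 7.2.1 describes the hematological events of JAK2 inhibitors as dose dependent. Under Table 4, a liver-test abnormality of Grade 3 or higher that recurs after a dose reduction ends fedratinib permanently, so an avoidable increase could cost the subject the drug. Grade 3 or 4 ALT, AST or bilirubin elevation is also an adverse event of special interest (Section 10.7.1).

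**Working it through.** The plan gives no figure on this point to reproduce. The check traces dose paths through the two rules.

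**Inputs**

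- Starting and maximum dose: 400 mg daily (Sections 7.2 and 7.2.1).
- One dose level: 100 mg daily (Table 4).
- Dose with a strong CYP3A4 inhibitor: 200 mg daily (7.2.2).
- Dose after the inhibitor stops: 300 mg for 2 weeks, then 400 mg as tolerated (7.2.2).
- Liver row of Table 4: hold; if the event recovers to Grade 1 or lower within 14 days, resume one level lower, with no later increase.

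**Formulas**

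Excess = dose directed by 7.2.2 − dose held before the inhibitor. Relative excess = excess / dose held before the inhibitor.

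**Paths**

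| Subject | Before inhibitor | With inhibitor | First 2 weeks after | Thereafter | Final excess |
|---|---|---|---|---|---|
| No toxicity | 400 mg | 200 mg | 300 mg | 400 mg | 400 − 400 = 0 mg |
| Grade 3 ALT on 400 mg, recovered within 14 days | 400 − 100 = 300 mg, increase barred | 200 mg | 300 mg | 400 mg | 400 − 300 = 100 mg (100/300 = 33%) |

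In the second path the 300 mg step only restores the earlier dose (300 − 300 = 0 mg). The conflict arises at the 400 mg step alone.

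**Which rule prevails**

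Table 4 prohibits the increase because of a past event. Section 7.2.2 directs the increase and conditions its last step on tolerance. The text of 7.2.2 does not carry the Table 4 prohibition over, and neither 7.2.1 nor 8.3.1 settles the order.

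**With a cap**

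If the final dose is the smaller of the pre-inhibitor dose and any Table 4 limit, the first path still ends at 400 mg and the second ends at min(400, 300) = 300 mg. The excess is 0 mg in both.

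**The case against.** The strongest reply is that the two rules serve different purposes and can both be followed. Table 4 manages toxicity, while 7.2.2 reverses a reduction made for a drug interaction. Section 7.2.2 says what should be done and Table 4 says what is not permitted, so a careful site would treat Table 4 as the ceiling. The as-tolerated condition is attached to the 400 mg step itself, which is the only excess step for a subject fixed at 300 mg. Safety monitoring and the Medical Monitor are also available.

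Much of this stands, and it limits the practical risk. It does not remove the gap. Current tolerance is a different test from a bar based on past toxicity. Contact with the Medical Monitor is invited, not required before an increase. The precedence of Table 4 has to be inferred.

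A reader might infer three stronger points, which the documents do not support:

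- *A subject fixed at 200 mg would be doubled to 400 mg.* The arithmetic is simple (400 − 200 = 200 mg; 200/200 = 100%), but 7.2.2 presupposes a reduction to 200 mg, and a subject already there has nothing to reduce. The liver row alone fixes a subject starting at 400 mg only at 300 mg, because recurrence after reduction means discontinuation. The 200 mg case is therefore less clear, and the point does not rest on it.
- *The Protocol Summary forbids any increase not listed in Table 4.* It does say "Reescalation of doses is possible in certain cases as defined in the Fedratinib Dose Modification Schedule table", but that sentence closes a paragraph on drug toxicity. Applied to every increase, it would also forbid 7.2.2 for subjects who had no toxicity.
- *The 2-week step in 7.2.2 contradicts Table 4's pace.* Table 4 does have "Subsequent upward dose titration possible of 1 dose level (100 mg daily) per cycle", but that governs re-challenge after Grade 4 hematological toxicity. Removing an interaction-based reduction is a different situation.

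**Conclusion.** The gap is real and narrow. As written, 7.2.2 can take a subject whom Table 4 has fixed at 300 mg up to 400 mg, an excess of 100 mg or 33%. This is a stated rule that gives the wrong dose for a definable group.

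The conclusion assumes that 7.2.2 is followed literally and that the subject tolerates 300 mg well enough for the 400 mg step to be taken. Three things must coincide: a strong inhibitor that could not be replaced, a Table 4 event that bars upward titration, and later withdrawal of the inhibitor. The documents do not say how often this happens. It is probably uncommon, and no estimate is offered.

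A reader might also look for an effect on the spleen response rate or the sample size. None follows: no endpoint, power figure or analysis changes. This is a dosing-clarity and safety point worth correcting at the next opportunity.

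**What to change.** Keep the present sequence in 7.2.2, including the as-tolerated condition, and add:

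> The dose must not exceed the dose taken before the inhibitor was started (400 mg if the inhibitor was already in use at Cycle 1 Day 1) or any lower limit set by Table 4; where Table 4 bars upward titration, do not increase above that level. If a Table 4 event occurred during co-administration, consult the Medical Monitor before any increase, and follow Table 4 for timing.

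The parenthesis is needed because exclusion criterion 8 (Section 4.3) bars CYP3A4 inducers and dual CYP2C19/CYP3A4 inhibitors but does not bar strong CYP3A4 inhibitors as such. A subject may therefore enter on one and have no pre-inhibitor fedratinib dose. The last sentence covers toxicity that arises while the inhibitor is being taken, including a first Grade 4 hematological event. For that event Table 4 allows re-escalation, but under its own timing.

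Subjects who were on 400 mg before the inhibitor and had no Table 4 event keep the current schedule. The cost is two sentences in the next amendment, IRB/EC approval under Section 13.5 and a note to sites. No visits, procedures or subjects are added.
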